6.7 Appropriateness of Measurements

All clinical and laboratory procedures that will be used in this study are standard and generally accepted.

6.8 Data Quality Assurance

Detailed procedures will be separately provided in the data management, monitoring, and quality plans.

6.8.1 Data Collection

Data of all subjects who gave informed consent have to be reported on the eCRFs in an anonymous fashion. Subjects are identified only by screening number.

The investigator will be responsible for the completeness, accuracy, and legibility of the information in the eCRF and other study documents. For documents other than eCRF, only ballpoint pen is to be used and any change of data is to be done by striking out the incorrect data with a single line and dating and initialing the changes made.

The study monitors then have to check the eCRFs against the source documents for accuracy and validity as per the monitoring schedule, as applicable. Any data recorded directly on the eCRF (for example, no prior written or electronic record of data) are considered source data. Also, any step in creation of source data is to be identified at which a computerized system is to be used to create, modify, maintain, archive, retrieve, or transmit source data.

The subject diary will remain as source at site and will only be source data verified by the monitors but not collected. Source data verification will include the diary data, eCRF data, and drug accountability of blisters.

Upon completion of the examination, eCRF completion is expected at each site to ensure quality of data and subject safety. Once eCRFs are completed, they will be available for review by the monitor and the designated CRO Clinical Data Management department. Completed eCRFs will be reviewed remotely for logical discrepancies. The monitor will ensure that all data queries and subsequent amendments in the eCRF documentation are made according to GCP guidelines.

A copy of the eCRF is to be archived by the investigator together with the study documents, source data, and laboratory records for the time required by the national regulation.

Confidentiality/Property

Adequate records have to be maintained for the study, including subject medical records, eCRFs, laboratory reports, worksheets, nursing notes, signed informed consent forms, product forms, SAE forms, and information regarding subject discontinuation and reasons for discontinuation. The confidentiality of each record with subject identification is to be guaranteed by the clinical investigator.

This study protocol and other study documents contain trade secrets and commercial information that is privileged and confidential. Such information is not to be disclosed unless required by laws or regulations. The investigator agrees to use this information only in conducting this study and is not allowed to use it for other purposes without written consent from the Sponsor. Results obtained from this study are the property of the Sponsor.

Retention of Records

The investigator agrees to retain copies of the eCRFs (usually on compact discs) with other study documents (e.g., the protocol and any protocol amendments, IEC approval, signed consent forms, and source documents for each subject in the study [eg, all demographic and medical information, including laboratory data, ECG, medication disposal and subject diaries]) in a secure place as long as needed to comply with national and international regulations (generally for 5 years). These records have to be made available for inspection upon reasonable request by a representative of the Sponsor or regulatory authorities.

In the event the investigator retires, relocates, or for any other reason withdraws from the responsibility for maintaining records for the period of time required (e.g. lack of storage capabilities), custody of the records has to be transferred to any other person who accepts responsibility for the records, e.g., a third party, an Institutional Review Board, or another investigator. Notice of such transfer has to be given in writing to the sponsor in advance.

Routine Monitoring

For protocol monitoring and compliance, a site visit will be held prior to initiation of subject enrolment. The protocol, eCRFs, study treatment supplies, and study procedures will be explained in detail.

The purpose of monitoring is to verify the rights and well-being of human subjects are protected; that study data are accurate, complete, and verifiable with source data; and that the study is conducted in compliance with the protocol, GCP, and the applicable regulatory requirements.

A monitor assigned by the CRO will conduct regular site visits for the purpose of study monitoring.

The investigator must agree to allow the study monitor and authorised representatives of the CRO or the sponsor to inspect all eCRFs and corresponding source documents (e.g., original medical records, subject records and laboratory raw data); to allow access to the clinical supplies, dispensing, and storage areas; and to agree to assist with their activities, if requested. The investigator should provide adequate time and space for monitoring visits.

The monitor will query any missing or spurious data with the investigator, which should be resolved in a timely manner. A monitoring log will be maintained to record each visit, the reason for the visit, the monitor's signature, and the investigator's or designee's confirmation signature.

6.8.2 Site Audits

The sponsor or its designee may carry out an audit at any time. Investigators will be given adequate notice before the audit occurs. The purpose of an audit is to confirm that the study is conducted as per protocol, GCP and applicable regulatory requirements, that the rights and well-being of the subjects enrolled have been protected, and that the data relevant for the evaluation of the investigational product have been captured, processed and reported in compliance with the planned arrangements. The investigator will permit direct access to all study documents, drug accountability records, medical records, and source data.

Regulatory authorities may perform an inspection of the study, even up to several years after its completion. If an inspection is announced, the investigator or the site must inform the sponsor immediately.

6.8.3 Database Management and Quality Control

The CRO will be responsible for the activities associated with the data management of this study, including the production of an eCRF, setting up a relevant database, along with appropriate validation of data and resolution of queries. All data will be entered into an eCRF. Automated and manual checks will be made against the data entered

into eCRF to ensure completeness and consistency. Resolution of queries will be implemented in the database.

AEs will be standardised for terminology and classification, using Medical Dictionary for Regulatory Activities (MedDRA). Concomitant medications will be classified by site of action and therapeutic and clinical characteristics using the World Health Organisation (WHO) DRUG dictionary. Versions of the dictionaries to be used will be documented in the Data Management Plan and the statistical analysis plan (SAP).

6.9 Statistical Methods and Determination of Sample Size

6.9.1 Statistical and Analytical Plans

Full details will be given in the SAP before database lock.

6.9.1.1 General Considerations

All significance tests will be carried out at a 5%, 2-sided significance level. Statistical tests will be supported by presenting estimates and 95% confidence intervals for the respective treatment effects and differences between the treatment groups. These estimates, confidence intervals and p-value will be based on the respective statistical models used for the analysis.

6.9.1.2 Handling of dropouts and missing data

The last observation carried forward (LOCF) approach will be implemented to replace missing efficacy values excepting postprandial parameters for all those subjects who do not present a data value at Week 12 and Week 24. Baseline value will not be used to impute missing data.

6.9.1.3 Analysis Populations

Randomized Set: The Randomized Set includes all subjects who randomized.

Safety Analysis Set: The Safety Analysis Set includes all subjects in the randomized set who have received at least one dose of study medication during the double-blind treatment period and have at least one post-baseline safety observation.

Full Analysis Set: The Full Analysis Set (FAS) includes all subjects in the randomized set who have received at least one dose of study medication during the double-blind treatment period and have at least one post-baseline efficacy observation. Subjects who were not diagnosed type 2 diabetes mellitus will be excluded.

Per-Protocol Set: The Per-protocol Set (PPS) includes subjects in the FAS who have no major protocol violations, who have completed at least 8 weeks of double-blinded

medication and who have > 75% treatment compliance with the investigational product (MP-513 or placebo) during the Double-blind treatment period. All protocol violations will be defined in more detail in the blind review document at a Blind Data Review Meeting that will be held before database lock.

6.9.1.4 Demography and Baseline Characteristics

Demography and Baseline Characteristics summaries will be based on FAS and the Safety Analysis Set unless otherwise indicated. No formal statistical test would be performed to determine statistical significance between treatment groups.

6.9.1.5 Efficacy Parameters

(1) Primary efficacy endpoint

The primary efficacy endpoint is the change in HbA1c from baseline to Week 24.

Primary analysis: The change in HbA1c from baseline to Week 24 between treatment groups will be analysed using analysis of covariance (ANCOVA), with treatment as fixed effect and baseline value as a covariate. Missing values at Week 24 will be imputed using LOCF approach. Primary analysis on primary efficacy endpoint will be presented for FAS.

Supportive analysis:

The same statistical methodology as described for primary analysis will be performed for PPS.

The change in HbA1c from baseline to Week 24 between treatment groups will be analysed using mixed-effects model for repeated measures, with treatment, visit and interaction of treatment and visit as fixed effects and baseline value as a covariate. An unstructured covariance matrix will be used to model the covariance of within-patient scores. No imputation will be implemented for missing values. This analysis will be presented for FAS.

(2) Secondary efficacy endpoint

The secondary efficacy endpoints are the change in FPG from baseline to Week 24.

The same statistical methodology as described for primary analysis on primary efficacy endpoint will be used. Analyses on secondary efficacy endpoint will be presented for FAS.

(3) Other efficacy endpoints

The other efficacy endpoints are;

- Proportion of subjects who achieved HbA1c < 7.0% at Week 24
- Change in fasting insulin, C-peptide, and glucagon from baseline to Week 24
- Change in HOMA-IR and HOMA-β from baseline to Week 24
- Change in body weight from baseline to Week 24
- Change in body weight from baseline to Week 12

For the proportion of subjects who achieved HbA1c < 7.0% at Week 24, the comparison between treatments will be performed using logistic regression with treatment as fixed effect and baseline value as a covariate. The subjects who has HbA1c ≤ 7.0% at baseline will be excluded from the analysis.

For the others, the same statistical methodology as described for primary analysis on primary efficacy endpoint will be used. Analyses on other efficacy endpoint will be presented for FAS.

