
Test and Reference Product, Dose, and Mode of Administration:
		

Sponsor: Mitsubishi Tanabe Pharma Corporation	Name of Medical Product: MP-513	Active Ingredient(s): Teneligliptin
MP-513 Form: Film-coated tablet for oral administration Strength: 20 mg and matching placebo during the placebo run-in period of 2 weeks, 1 tablet of single-blinded study treatment (placebo tablet) will be orally administered once daily before breakfast. During the double-blind treatment period of 24 weeks, 1 tablet of double-blinded study treatment (20 mg tablet or placebo tablet) will be orally administered once daily before breakfast.		

Sponsor: Mitsubishi Tanabe Pharma Corporation	Name of Medical Product: MP-513	Active Ingredient(s): Teneligliptin

Criteria for Evaluation: The study objective is to evaluate the efficacy and safety of MP-513 compared with placebo in Chinese subjects with type 2 diabetes mellitus inadequately controlled with diet and exercise.
 
Primary efficacy endpoint:
 
 • Change in HbA1c from baseline to Week 24 
Secondary efficacy endpoint:
 
 • Change in FPG from baseline to Week 24 
Other efficacy endpoints:
 
 • Proportion of subjects who achieved HbA1c < 7.0% at Week 24 • Change in fasting insulin, C-peptide, and glucagon from baseline to Week 24 • Change in Homeostatic Model Assessment- Insulin resistance (HOMA-IR) and HOMA-β from baseline to Week 24 • Change in body weight from baseline to Week 24 • Change in HbA1c and FPG from baseline to Week 12 
Safety Endpoints
 
 • Adverse Events (AEs) • Adverse drug reactions (ADRs) • Hypoglycaemic episodes • Cardiovascular events • Vital signs (blood pressure, pulse rate and body temperature) • Laboratory measurements • 12-lead ECG 		
Statistical Methods:		

Sponsor: Mitsubishi Tanabe Pharma Corporation	Name of Medical Product: MP-513	Active Ingredient(s): Teneligliptin

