6.3 Baseline Assessments

Baseline assessments will be the most recent assessment prior to the randomization.

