8.3 Analysis Populations

The study will use following analysis populations for data summarization. Number and percentage of subjects in each analysis set will be summarized by treatment group and overall.

Table 6: Analysis Population

Population	Definition	Displays	Note
All Subject Set	The All Subject Set includes all subjects who were screened	Displays on subject disposition	The subjects will be analyzed for disposition
Randomized Set	The Randomized Set includes all subjects who were randomized	Displays on subject population and	The subjects will be analyzed according to the treatment to which they were randomized to, irrespective of treatment received
Full Analysis Set (FAS)	The FAS includes all subjects in the randomized set who have received at least one dose of study medication during the double-blind treatment	Displays related to demography, other baseline characteristics and	The subjects will be analyzed according to the treatment to which they were randomized

Population	Definition	Displays	Note
	period and have at least one post-baseline efficacy observation. Subjects who were not diagnosed with type 2 diabetes mellitus will be excluded.	all efficacy analyses	to, irrespective of treatment received
Per-Protocol Set (PPS)	The PPS includes subjects in the FAS who have no major protocol violations, who have completed at least 8 weeks of double-blinded medication and who have > 75% treatment compliance with the investigational product (MP-513 or placebo) during the Double-blind treatment period.	Demographics and Primary efficacy analysis	All protocol violations will be defined in more detail in the blind review document at a Blind Data Review Meeting that will be held before database lock. The subjects will be analyzed according to the treatment to which they were randomized to, irrespective of treatment received.
Safety Analysis Set	The Safety Analysis Set includes all subjects in the randomized set who have received at least one dose of study medication during the double-blind treatment period.	Displays related to demography, other baseline characteristics and all safety analyses	The subjects will be analyzed as MP-513 if the subjects received MP-513 at least once, irrespective of treatment to which they were randomized to. In other cases, the subjects will be analyzed according to the treatment they were randomized to.

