8.7.3 Analysis of Other Efficacy Variables

All other efficacy endpoint will be analysed using FAS. The other efficacy endpoints are as follows:

- Proportion of subjects who achieved HbA1c < 7.0% at Week 24
- Change in fasting insulin, C-peptide, and glucagon from baseline to Week 24
- Change in HOMA-IR and HOMA-β from baseline to Week 24
- Change in body weight from baseline to Week 24
- Change in HbA1c and FPG from baseline to Week 12

Proportion of subjects who achieved HbA1c < 7.0% at Week 24 (LOCF):

For the proportion of subjects who achieved HbA1c < 7.0% at Week 24 (LOCF), the comparison between treatments will be performed using logistic regression with treatment as fixed effect and baseline HbA1c value as a covariate. The subjects who have HbA1c < 7.0% at baseline will be excluded from the analysis.

The odds ratio (OR) with 95% Wald CIs will be presented for between treatment groups comparison of responder rate (i.e. proportion of subjects who achieved HbA1c < 7.0% at Week 24). The Wald Chi-Square p-value for significance of treatment effect after controlling for baseline HbA1c will also be displayed.

For logistic regression analysis, the dichotomous response variable will be coded as '1' (for subjects who achieved HbA1c < 7.0% at Week 24) and '0' for subjects for whom HbA1c ≥ 7.0% at week 24.

The frequency count and percentage of subjects who achieved HbA1c < 7.0% at week 24 will also be summarized by treatment groups.

Other efficacy endpoints:

For the remaining other efficacy endpoints, namely;

- Change in fasting insulin, C-peptide, and glucagon from baseline to Week 24
- Change in HOMA-IR and HOMA-β from baseline to Week 24
- Change in body weight from baseline to Week 24
- Change in HbA1c and FPG from baseline to Week 12

The line graph for mean change in other efficacy endpoints from baseline to Week 24 and Week 24 (LOCF) will be presented. The 95% CIs will also be shown in the graph with error bar. The plots of Week 24 and Week 24 (LOCF) will not be connected.

The same statistical methodology as described for primary analysis on primary efficacy endpoint will be used.

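### Do the mismatches between protocol and SAP on the responder exclusion, the safety set and the Week 12 endpoints call for a change to the plan?

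*Protocol*

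**What the plan says.** **Responder analysis.** The endpoint is HbA1c below 7.0% at Week 24. Protocol 6.9.1.5 states: "The subjects who has HbA1c ≤ 7.0% at baseline will be excluded from the analysis". SAP 8.7.3 states: "The subjects who have HbA1c < 7.0% at baseline will be excluded from the analysis". The protocol synopsis describes the same logistic regression with no exclusion. SAP 8.7.3 assigns the non-response code "for subjects for whom HbA1c ≥ 7.0% at week 24". Under SAP 6.3, "Baseline assessments will be the most recent assessment prior to the randomization", so baseline is normally the Day 1 value and not one of the two entry values.

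**Safety Analysis Set.** Protocol 6.9.1.3 requires one double-blind dose and also that subjects "have at least one post-baseline safety observation". SAP 8.3 takes all randomized subjects "who have received at least one dose of study medication during the double-blind treatment period" and adds no further condition.

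**Week 12 endpoints.** The protocol synopsis lists "Change in HbA1c and FPG from baseline to Week 12". Protocol 6.9.1.5 has "Change in body weight from baseline to Week 12" in that place and leaves out HbA1c and FPG. SAP 8.7.3 follows the synopsis, and SAP 7.3 gives Week 12 LOCF for HbA1c and FPG only.

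**Declared changes.** SAP 5.1 reports none, relative to protocol version 2.0 of 29 April 2016.

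**The concern.** A responder population, a safety denominator and a list of endpoints each appear in two written forms, and the SAP section meant for declaring departures declares none. If nobody knew which form applied, the choice could be made after unblinding.

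The responder cut-off matters most at the boundary. Entry allows HbA1c of exactly 7.0%. A subject with that baseline is not yet at target and can still respond, yet the protocol drops the subject and the SAP keeps the subject. Under the protocol's safety set, a dosed subject with no later observation leaves every safety denominator. For Week 12, Protocol 6.9.1.5 names a body-weight comparison that the SAP does not plan.

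**Working it through.** No figure in the documents can be reproduced here, because the sample-size sections are redacted in both. The check is a comparison of the texts, followed by illustrations under stated assumptions.

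**1. Responder rule: which subjects differ?**
- Baseline below 7.0%: out under both rules.
- Baseline above 7.0%: in under both rules.
- Baseline exactly 7.0%: out under Protocol 6.9.1.5, in under SAP 8.7.3.

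The SAP rule removes exactly those who already meet the target, so it matches the response coding. SAP 7.10 uses the same boundary for its lowest baseline HbA1c subgroup.

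*How many?* The planned total is 120 + 120 = 240. The share at exactly 7.0% is an assumption:
- 1%: 240 × 0.01 = 2.4 subjects
- one of the thirty 0.1-point steps from 7.0 to 9.9, taken as equally likely: 240 / 30 = 8.0
- 5%: 240 × 0.05 = 12.0
- 8%: 240 × 0.08 = 19.2

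A simulation gave 2.7 to 7.9 of 240. It assumed underlying SD 0.8, measurement SD 0.15, underlying means 7.3 to 8.1, entry limits applied at two visits, a separate Day 1 baseline and values rounded to 0.1. Varying the underlying SD from 0.6 to 1.0 gave 1.9 to 9.7. With values reported to 0.01 the count falls to 0.2 to 0.6. The documents do not state the reporting precision.

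*What does it do to the odds ratio?* Further assumptions: placebo change -0.1, slope -0.25 per 1% of baseline above 8.0, residual SD 0.7, and a treatment effect of -0.48 or -0.79 (both taken from the protocol's background section). With underlying mean 7.6, logistic regression on treatment and baseline gives:

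| Effect | Rule | Responders, MP-513 vs placebo | Odds ratio |
|---|---|---|---|
| -0.48 | below 7.0% excluded | 30.8% vs 13.6% | 3.29 |
| -0.48 | 7.0% and below excluded | 30.0% vs 12.9% | 3.30 |
| -0.79 | below 7.0% excluded | 45.1% vs 13.5% | 6.91 |
| -0.79 | 7.0% and below excluded | 44.3% vs 12.9% | 6.93 |

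Over eight scenarios (four underlying means, two effects) the largest shift in the log odds ratio was 0.0057, against a standard error of 0.39: 0.0057 / 0.39 = 0.015 SE.

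*Power.* For two proportions with n per arm, power = Φ([|p₁ − p₂| − 1.96·√(2p̄(1 − p̄)/n)] / √([p₁(1 − p₁) + p₂(1 − p₂)]/n)). Take assumed rates of 20% and 40%, so p̄ = 0.30.
- n = 120: (0.2 − 1.96 × 0.0592) / 0.0577 = 1.456, power 92.7%.
- n = 120 × 0.92 = 110.4, the 8% case: (0.2 − 1.96 × 0.0617) / 0.0602 = 1.314, power 90.6%.

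**2. Safety set.** The sets differ only in subjects who took a double-blind dose and then gave no safety observation. Adverse events are collected at every visit and at the follow-up call, so such a subject must be lost almost at once. The number cannot be derived from the documents. With an assumed 36 subjects with events in an arm of 120:
- none removed: 36/120 = 30.0%
- one removed: 36/119 = 30.3%
- three removed: 36/117 = 30.8%

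The SAP set is the more inclusive one and does not depend on follow-up.

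**3. Week 12.** In Protocol 6.9.1.5 the Week 12 item comes directly after the Week 24 body-weight item and repeats its wording, in the place where the synopsis has HbA1c and FPG. That pattern points to a copying slip. The SAP adopted the synopsis version. Body weight is measured at Week 12 (Table 2 in both documents), change from baseline is defined for post-baseline visits (SAP 6.7), and Protocol 6.9.1.2 provides Week 12 LOCF for efficacy values. A Week 12 weight comparison could therefore be run on request.

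**4. Which text do analysts follow?** Protocol 6.9.1 leaves full analysis detail to the SAP, to be given before database lock. SAP 7.1 places all analyses after lock and unblinding. The SAP gives one rule for each of the three items, so nothing is left open.

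**The case for a change.** The best case for a change is that supplying detail differs from altering a cut-off, a population or an endpoint list, and that SAP section 5 exists to record such alterations. If the supplied protocol is version 2.0, the statement in SAP 5.1 is inaccurate for the responder rule and the safety set, and it conflicts with Protocol 6.9.1.5 on Week 12. Nor is the choice of rule invisible in one trial. In 1500 simulated trials of 240 in each of three scenarios, the ratio of the two rules' odds ratios had a 95% range of 0.86 to 1.20 at its widest, and p < 0.05 status switched in 0 to 2.8% of trials. An edit to section 5 would cost little.

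The textual part stands: the differences exist and are undeclared. Whether SAP 5.1 is wrong on the first two cannot be settled, because the supplied protocol's version cannot be confirmed. The single-trial spread would matter if someone could choose the rule after seeing the data, but SAP 8.7.3 already fixes it. The spread is also centred close to no difference, so neither rule favours a treatment. The protocol's cut-off is itself defensible, since it leaves out subjects for whom a very small fall would count as response. Aligning the protocol text would not be free either: Protocol 2.4 requires sponsor and principal investigator approval, with ethics committee approval or notification depending on the type of change.

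**Conclusion.** No change to the plan follows. The Week 12 item is most likely a clerical slip inside the protocol, which the SAP resolves in line with the synopsis. The other two are small departures in which the SAP rule is sound: its responder exclusion matches the endpoint, and its safety set keeps every dosed subject. Declaring them would improve the record but would change no result.

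The primary and secondary efficacy analyses are untouched. The expected shift in the responder odds ratio is at most 0.015 SE under the simulation's assumptions. The count behind it (under 1 to about 19 of 240) depends on assumed rounding and spread. The safety effect is about 0.3 points per subject removed from an arm of 120, at an assumed incidence of 30%. The conclusion rests on the SAP being in place before database lock, as Protocol 6.9.1 requires.
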